8.2.4. Follow-up

Events that can define the start and end of FU are provided in Table 7. Follow-up will end at the earliest of all possible events that define the end of FU.

Safety event of interest	Events defining the start of follow-up	Events defining the end of follow-up ^a
General safety events ^b		
	 Index date (if the risk interval starts on day 0), or One day after the index date (if the risk interval starts on day 1; see Table 8 in Section 8.3.2.1 for outcomespecific risk windows) 	 End of the study period End of data availability Disenrollment from the health plan Death Occurrence of the safety event of interest End of duration of the outcome-specific risk window (maximum of 1 year; see Table 8 in Section 8.3.2.1 for outcome-specific risk windows) Receipt of any brand of COVID-19 vaccine^c
Pregnancy safety outcomes		
Spontaneous abortion	 One day after the index date (if the index date is on or after estimated pregnancy start), or Estimated pregnancy start 	 End of pregnancy 20 weeks of gestation Receipt of and brand of COVID-19 vaccine^c

 Table 7.
 Events defining the start and end of follow-up

Safety event of interest	Events defining the start of follow-up	Events defining the end of follow-up ^a
Stillbirth	 One day after the index date (if the index date is on or after estimated pregnancy start) or Estimated pregnancy start 	 End of pregnancy Receipt of any brand of COVID-19 vaccine^c
Preterm birth	 One day after the index date (if the index date is on or after estimated pregnancy start) or Estimated pregnancy start 	 End of pregnancy 37 weeks of gestation Receipt of any brand of COVID-19 vaccine^c
Major congenital malformations ^d	• Day of birth	 End of study period End of data availability Disenrollment from the health plan Death Diagnosis of major congenital malformation Age 1 year
Small size for gestational age ^d	• Day of birth	• Predefined period shortly after birth (specific period to be defined in the SAP)

Table 7.	Events defining the start and end of follow-up
----------	--

COVID-19 = coronavirus disease 2019; FU = follow-up; SAP = statistical analysis plan.

a. For all analyses, the earliest of the listed events following the index date will mark the end of FU for each outcome. If FU ends due to the occurrence of a particular safety event of interest, FU will continue for all other safety events.

[figure not shown]
b. Safety events of interest are listed in Table 8 in Section 8.3.2.1.

c. For analyses of the primary series (doses 1, 2, and 3) only: If dose 2 is Pfizer-BioNTech original monovalent COVID-19 Vaccine, individuals will stop FU in the dose 1 cohort and may start FU in the dose 2 cohort. When the risk interval for dose 1 overlaps with the risk interval for dose 2 and the risk interval definition includes day 0, the date of receipt of dose 2 will be included in the FU for dose 1. Otherwise, the date of receipt of dose 2 will be included in the FU for dose 1. Otherwise, the date of receipt of dose 2 will be included in the FU for dose 3 is Pfizer-BioNTech original monovalent COVID-19 Vaccine, individuals will stop FU in the dose 2 cohort and may start FU in the dose 3 cohort. (Note that dose 3 will only be included in primary series analyses in individuals aged 6 months through 4 years and in individuals aged 5 years and older whose third primary series dose is received within 2 months of the second dose.)

d. Major congenital malformations and small size for gestational age will be assessed in the infant.

For illustrative purposes, Figure 1 depicts the timelines of hypothetical patients to show the concepts of eligibility for study cohorts and FU in primary series analyses of general safety events in the general population, immunocompromised individuals, or individuals with history of COVID-19. Figure 2 depicts the timelines of hypothetical patients to illustrate eligibility for the study cohorts and FU, using primary series analyses of spontaneous abortion as an example.

Figure 1. Hypothetical patients to illustrate eligibility for study cohorts and follow-up of general safety events in a primary series analysis among the general population, immunocompromised individuals, or individuals with a history of COVID-19

[figure not shown]

BNT162b2 = Pfizer-BioNTech original monovalent COVID-19 Vaccine; COVID-19 = coronavirus disease 2019; FU = follow-up.

Note: If FU ends due to the occurrence of a particular safety event of interest, FU will continue for all other safety events.

PFIZER CONFIDENTIAL CT24-WI-GL02-RF02 3.0 Non-Interventional Study Protocol Template For Secondary Data Collection Study 20-May-2021 Page 65 of 120

Figure 2. Hypothetical patients to illustrate eligibility for study cohorts and follow-up of spontaneous abortion events in a primary series analysis in pregnant

PFIZER CONFIDENTIAL CT24-WI-GL02-RF02 3.0 Non-Interventional Study Protocol Template For Secondary Data Collection Study 20-May-2021 Page 66 of 120 BNT162b2 = Pfizer-BioNTech original monovalent COVID-19 Vaccine; COVID-19 = coronavirus disease 2019; FU = follow-up.

a. End of the exposure window is 20 weeks of gestation or pregnancy end, whichever is earlier.

8.3. Variables

8.3.1. Vaccine exposures

The primary exposure of interest is Pfizer-BioNTech original monovalent COVID-19 Vaccine. Receipt of Pfizer-BioNTech original monovalent COVID-19 Vaccine will be identified in data from claims and electronic health records (where available, as not all data research partners will have access to electronic health records) via procedure codes or pharmacy dispensing codes, which will be specified in the SAP. Although vaccine administration codes distinguish between dose number (e.g., first, second, third, booster dose), it is anticipated that most vaccinations will be identified with codes that do not provide information on dose number. If feasible (to be determined during the monitoring phase of the study), dose number will be assigned based on vaccine administration codes. Otherwise, dose number will be assigned based on the ordinal number of the vaccinations (i.e., first, second, or third) recorded in the data sources, which would require that individuals be enrolled from the time of authorization of Pfizer-BioNTech original monovalent COVID-19 Vaccine. Where existing linkages with immunization registries are available for use in research studies within the appropriate participating research databases, immunization registry data will be combined with data from claims and electronic health records to identify vaccine exposures.

Receipt of other COVID-19 vaccines available in the US will be identified in a similar manner. COVID-19 vaccines available during the study period and codes will be documented in the SAP. Rules to handle de-duplication of codes and/or implausible spacing of doses (e.g., 2 codes for COVID-19 vaccine within 2 days) will be described in the SAP.

If COVID-19 vaccines are administered without reimbursement from health insurers, there is the potential that they will not be recorded in claims and electronic health records. This situation may lead to misclassification of truly exposed individuals as "unexposed" comparators, which will underestimate vaccine coverage rates and may bias comparative risk estimates for the cohort design with concurrent unexposed comparators. The completeness of exposure data will be assessed in monitoring analyses before the final analyses are conducted by comparing study data with publicly available estimates of vaccine coverage and/or estimates based on immunization registry data from select states (if available); if the coverage estimates differ meaningfully from the "benchmarking" estimates (based on to-be-defined criteria in the SAP), then modifications to the study approach may be considered. If this happens, the SCRI may be designated as the primary study designs and/or linkage to immunization registries may be considered if feasible.

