Based on data through 12 June 2021, the Vaccine Safety Datalink (VSD) observed in analyses based on 22 cases in the risk interval, that the age- and site-adjusted rate ratio for risk of myocarditis/pericarditis in the 7 days following mRNA vaccination in individuals aged 12 to 39 years was 10.0 (95% CI, 2.9-46.5). The corresponding rate ratio for Pfizer-BioNTech original monovalent COVID-19 Vaccine was 2.4 (95% CI, 0.4-24.9). In individuals aged 12 to 39 years, the incidence rate of myocarditis/pericarditis in the 21 days following mRNA vaccination was greater in males than in females and was greater following the second dose than following the first dose (12.6 cases per million second doses vs. 4.4 cases per million first doses). Additionally, a temporal clustering of myocarditis/pericarditis occurred within the week following vaccination, with the most likely cluster occurring 0 to 5 days following vaccination. Based on these data and a benefit-risk assessment, on 23 June 2021, the ACIP concluded that the benefits of vaccinating all recommended age groups with mRNA COVID-19 vaccine clearly outweighed the risks of vaccination, including the risk of developing myocarditis after vaccination. The ACIP emphasized the need to continue monitoring outcomes of myocarditis cases after COVID-19 vaccination and that providers and the public should be informed about these myocarditis cases and the use of COVID-19 vaccines. Based on the ACIP's conclusions, COVID-19 vaccination continued to be recommended for all individuals aged ≥ 12 years under the FDA's EUA. The FDA added this safety event to the EUA factsheet, and the warnings and precautions section of prescribing information for Pfizer-BioNTech original monovalent COVID-19 Vaccine states that, "Postmarketing data demonstrate increased risks of myocarditis and pericarditis, particularly within 7 days following the second dose. The observed risk is higher among males under 40 years of age than among females and older males. The observed risk is highest in males 12 through 17 years of age" (Pfizer, 2021).

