A main limitation of the cohort design with concurrent unexposed comparators is that it may be subject to misclassification of unexposed status, since many vaccinations occurring outside traditional medical care settings without health insurance reimbursement (e.g., mass vaccination campaigns by public health officials) may not be captured in administrative claims data. To address this limitation, sensitivity analysis will incorporate a self-controlled risk interval (SCRI) design for events with an acute onset and a short risk interval (Baker et al., 2015) (defined for the purposes of this study as ≤ 42 days after vaccination). If exposure information is deemed incomplete based on feasibility analysis during the monitoring phase,

PFIZER CONFIDENTIAL

CT24-WI-GL02-RF02 3.0 Non-Interventional Study Protocol Template For Secondary Data Collection Study 20-May-2021 Page 47 of 120 the primary study design may be switched to the SCRI design or linkage with data from immunization registries may be conducted (if feasible). Another limitation of the proposed approach is that outcomes may be misclassified in data from claims and electronic health records. To address this limitation, algorithms for select outcomes that may be susceptible to substantial misclassification may be validated through medical records or review of patient profiles (i.e., chronological listing of a patient's codes in data from claims and/or electronic health records) (see Section 8.3.2.2). The determination of which outcomes may be susceptible to substantial misclassification will be informed by clinical expert opinion and review of validation studies if available.

The study observation period will start on the date that Pfizer-BioNTech original monovalent COVID-19 Vaccine was granted EUA in the US (11 December 2020) and will end a minimum of 3 years after this date. Although only exposures identified through 18 April 2023 (the date that authorization of Pfizer-BioNTech original monovalent COVID-19 Vaccine ended) will be included in the study, outcomes occurring in the predefined risk period will be assessed after this date. The study will include both vaccinations received under the EUA and under the biologic license application (BLA).

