8.2.2.1. Primary series analysis

Primary series analyses in children aged 6 months through 4 years will include doses 1, 2, and 3. Details for handling the timing between individual doses in this age group will be described in the statistical analysis plan (SAP). Primary series analyses in individuals aged 5 years and older will include dose 1 and 2 as well as dose 3 if received within 2 months of dose 2.

To be included in the primary series analysis of Pfizer-BioNTech original monovalent COVID-19 Vaccine receipt among the general population, the population of immunocompromised individuals (individuals with immunodeficiencies, immunosuppressant medication use, HIV and other immunosuppressing conditions, and/or receipt of organ or bone marrow transplant), and the population of individuals with a history of COVID-19, individuals older than 1 year of age must have had continuous medical and pharmacy insurance coverage for at least 12 months before each index date (as defined in Table 1 below and Table 2 in Section 8.2.2.2) or from the earliest date that they were eligible to receive the vaccine until the index date—whichever period is longer. Children aged younger than 12 months on the index date must be enrolled from birth until the index date.

Depending on whether data on vaccine dose number are recorded in the data sources, additional enrollment may be required from the earliest authorization of the Pfizer-BioNTech original monovalent COVID-19 Vaccine (i.e., 11 December 2020) to enable dose number identification. The feasibility of determining dose number based on vaccine codes will be confirmed during the monitoring phase of the study, and all eligibility criteria will be fully documented in the SAP.

A separate exposed cohort will be formed for each dose. A separate unexposed cohort will be formed for each of the exposed cohorts to serve as comparator cohorts. The criteria for the cohorts for primary series analyses of the general population, immunocompromised individuals, and individuals with a history of COVID-19 are described in Table 1.

Table 1.Cohort definitions for primary series analysis of the general population,
immunocompromised individuals, and individuals with a history of
COVID-19

Cohort	Inclusion criteria	Index date	Exclusion criteria
Dose 1 exposed	Record of a first dose in the primary series of Pfizer-BioNTech original monovalent COVID-19 Vaccine	Date of first dose	Record of any COVID-19 vaccine before the index date

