Finally, analyses of third doses of Pfizer-Bio-N-Tech COVID-19 Vaccine (either as an additional dose in a primary series or as a booster dose) may be limited by small numbers of third dose recipients. A large proportion of individuals may be excluded from these analyses if many individuals do not have available information on dose number, as enrollment from the beginning of the authorization of COVID-19 vaccines would be needed to enable dose number identification. The overall number of pregnant women included in the analysis of third doses may be low due to lower COVID-19 vaccine uptake in pregnant women and because pregnant women will be identified by their pregnancy outcomes, which means that

PFIZER CONFIDENTIAL

CT24-WI-GL02-RF02 3.0 Non-Interventional Study Protocol Template For Secondary Data Collection Study 20-May-2021 Page 100 of 120 women will not be identified as pregnant and eligible to be included in the population of pregnant women until months after they give birth or their pregnancy otherwise ends.

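### The fallback rule counts recorded vaccinations to assign dose number, with enrolment as its only stated condition, so a dose missed while enrolled shifts later doses down and mixes the dose-specific estimates

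*Protocol*

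**What the plan says.** Section 8.3.1 prefers to read dose number from vaccine administration codes, if the monitoring phase shows that this is feasible. The same section doubts that it will be: "it is anticipated that most vaccinations will be identified with codes that do not provide information on dose number". Failing that, the rule is that "dose number will be assigned based on the ordinal number of the vaccinations (i.e., first, second, or third) recorded in the data sources". A single condition, enrolment, is attached to this rule: "which would require that individuals be enrolled from the time of authorization of Pfizer-BioNTech original monovalent COVID-19 Vaccine".

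The eligibility text ties dose number to enrolment in the same way. Section 8.2.2.1 says "additional enrollment may be required from the earliest authorization of the Pfizer-BioNTech original monovalent COVID-19 Vaccine (i.e., 11 December 2020) to enable dose number identification", with parallel statements in Sections 8.2.2.2 and 8.2.3.2. In the limitations (Section 8.9), "enrollment from the beginning of the authorization of COVID-19 vaccines would be needed to enable dose number identification".

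On capture, Section 8.1 warns that "many vaccinations occurring outside traditional medical care settings without health insurance reimbursement (e.g., mass vaccination campaigns by public health officials) may not be captured". Section 8.7.3.1 repeats the warning for the early roll-out, and Section 8.3.1 acknowledges the potential for unrecorded doses.

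Dose number defines the cohorts in Tables 1, 2, 4 and 5, and Section 8.7.2.2 estimates the comparative risks separately by dose.

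**The concern.** Enrolment shows that a person was insured. It does not show that each dose produced a claim. The unreimbursed doses that the protocol worries about are given to people who are enrolled at the time, so the enrolment condition does not deal with them. The order of recorded doses equals dose number only when every earlier dose was recorded.

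Two kinds of error follow. If the first dose is missed, the true second dose enters the dose 1 exposed cohort, because Table 1 excludes only people with a prior record. If one of the two earlier doses is missed, a true third dose can be counted as a second. It would then be compared with people who have no recorded vaccine (Table 1) and not with two-dose recipients (Table 2).

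The protocol draws only one consequence from missed doses: exposed people end up among the unexposed. Wrong dose number is not named in Sections 8.3.1, 8.7.3.1 or 8.9. At stake are the dose-specific relative risks of primary objectives 1 to 3, and the myocarditis/pericarditis results by dose number in Section 8.3.3.3, where Section 6 itself reports a difference between doses.

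**Working it through.** **The plan's own figures.** None is disputed. The Section 8.5 example reproduces: expected comparator events 5,000,000 × 2 × (21/365.25) × 10/100,000 = 57.5; exposed events 1.4 × 57.5 = 80.5; probability Φ[ln(2.5/1.4)/√(1/57.5 + 1/80.5) − 1.96] = 0.919, stated as 92%. It counts both doses together, so it says nothing about dose assignment.

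**Inputs.** Section 6 gives "12.6 cases per million second doses vs. 4.4 cases per million first doses" within 21 days, a ratio of 12.6/4.4 = 2.9. These rates are for any mRNA vaccine at ages 12 to 39, so they serve only as an illustration. The protocol gives no capture probability. Call it c and assume that each dose is recorded independently; c = 0.9, 0.8 and 0.6 are assumptions.

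**Two true doses.** A recorded first dose is true dose 1 with weight c, and true dose 2 with weight (1 − c)c. The share that is truly dose 2 is therefore s = (1 − c)/(2 − c). The apparent dose 1 rate is 4.4 + s × (12.6 − 4.4). A recorded second dose can only be true dose 2, so its rate stays at 12.6.

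| c | s | apparent dose 1 rate per million | change from 4.4 | dose 2 / dose 1 |
|---|---|---|---|---|
| 1.0 | 0 | 4.4 | none | 2.9 |
| 0.9 | 0.1/1.1 = 9% | 4.4 + 0.0909 × 8.2 = 5.1 | +17% | 2.4 |
| 0.8 | 0.2/1.2 = 17% | 4.4 + 0.1667 × 8.2 = 5.8 | +31% | 2.2 |
| 0.6 | 0.4/1.4 = 29% | 4.4 + 0.2857 × 8.2 = 6.7 | +53% | 1.9 |

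**Three true doses.** A recorded second dose is true dose 2 with weight c², and true dose 3 with weight 2c²(1 − c). The share that is truly dose 3 is 2(1 − c)/(3 − 2c): 17%, 29% and 44% at c = 0.9, 0.8 and 0.6. Of the recorded true third doses, only c² are counted as third: 81%, 64% and 36%.

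**If capture is not independent.** If only dose 1 can be missed, with probability m, and dose 2 is always recorded, the share is m itself. For m = 0.1, 0.2 and 0.4 the apparent dose 1 rate is 5.2, 6.0 and 7.7 per million, which is more mixing than above. If both doses are missed together there is no mixing, because the person has no record at all.

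**Do the planned checks detect it?**
- The completeness check in Section 8.3.1 compares coverage with benchmarks and leads to changes that are discretionary.
- Registry data are added only where a usable linkage already exists.
- The self-controlled analysis of the primary series (Section 8.7.3.2) combines risk time after all doses, so it cannot show whether doses were numbered correctly.

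**The case against.** The strongest reply is that the ordinal rule is only a fallback and has checks in front of it. Section 8.1 schedules monitoring-phase work on vaccine data completeness and on dose number availability. Section 8.3.1 allows registry linkage or a change of primary design. De-duplication, implausible spacing and full eligibility rules are left to the SAP. A spacing rule could flag a booster that follows a lone recorded dose by months, and Table 1 asks for a second dose within the primary series. This stands as mitigation, and the missing SAP detail is not counted against the protocol. But the checks are partial or discretionary, and none is directed at dose number. Spacing alone cannot settle it: Section 6 gives 3 weeks between doses 1 and 2 and at least 28 days before a third primary dose in immunocompromised people, so some sequences look alike.

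A reader might infer more than the text supports:
- **That many doses are never recorded.** The protocol says that they may not be captured, and only Section 8.7.3.1 points to the early roll-out.
- **That enrolment is declared sufficient.** It is called required or needed; the point is that no other condition is stated.
- **That the self-controlled design serves only exposure misclassification.** Sections 8.7.3.2 and 8.9 also give it a role against time-constant confounding.
- **That mixing will trigger the rule in Section 8.7.2.2 to combine doses with similar estimates.** This is not shown: even at c = 0.6 the ratio is 1.9.

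It is also fair to object that the table shows crude rates, while the estimand is a relative risk. The same missed doses place vaccinated people in the comparator, and the net effect was not computed.

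**Conclusion.** The point holds in a limited form. If dose-specific codes prove infeasible, which Section 8.3.1 makes likely, the stated rule measures dose number only when earlier doses were all recorded, and the protocol itself doubts that they were. Any missed earlier dose shifts later doses down in the dose-specific cohorts.

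The size cannot be derived from the document. Under independent capture of 0.9 to 0.6 and two doses, 9% to 29% of recorded first doses would be true second doses. On the any-mRNA rates for ages 12 to 39, the dose contrast would shrink from 2.9 to between 2.4 and 1.9. Correlated capture could make this smaller or larger, and the effect on the relative risk also depends on contamination of the comparator. The pooled estimate for at least one dose is less affected. Because a stated rule can bias estimates of primary objectives, this should be changed and is more than a gap in detail.

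**What to change.** 1. In Sections 8.3.1, 8.7.3.1 and 8.9, name dose-number misclassification as a separate consequence of incomplete capture. State that enrolment since authorization is necessary for the ordinal rule but does not by itself establish dose number.
2. Where dose-specific codes or existing registry linkage are available, cross-tabulate ordinal number against coded or registry dose number by calendar period. Use the table in a quantitative bias analysis of the dose-specific relative risks.
3. Add a sensitivity analysis restricted to doses whose number is confirmed by code or registry. Prior recorded doses and their intervals may support the confirmation but should not replace it.

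The cost is programming, one cross-tabulation and one further set of estimates, limited to records that carry a usable code or an existing linkage. The restricted analysis will be smaller and less precise, and it may be a selected subset, since most codes are expected to lack dose number. It therefore serves as a check on the main analysis, which stays as planned.
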